9. STUDY POPULATION

9.1 Subject Disposition

Subject disposition information will be summarized for all subjects by treatment group. Summaries will include: the number of subjects screened under protocol Version 2.0 and 2.1, the number of enrolled (randomized) subjects, the number of subjects in the safety population, the number of subjects discontinuing the study, and the primary reason for discontinuation.

9.2 Protocol Deviations

Protocol deviations will be evaluated as per the clinical database and additionally as tracked by operational study team members.

Protocol deviations due to COVID-19 will be summarized by treatment group. Missed assessments due to COVID-19 will be reported in a data listing.

9.3 Demographic and Baseline Characteristics

Demographic and baseline characteristics will be summarized descriptively for the safety population. Demographic characteristics will include age, ethnicity, and race. Age will be calculated in years relative to the informed consent date. Baseline characteristics will include height, weight, and body mass index (BMI).

9.4 Prior and Concomitant Medications

Prior and concomitant medication verbatim terms in the eSource forms will be mapped to Anatomical/Therapeutic/Chemical (ATC) class and preferred names using the WHODrug global dictionary (Version Sep, 2020).

Prior medications are those medications that started before the initial dose of study drug. Concomitant medications are those medications that started after the initial dose of study drug or medications that started before the initial dose of study drug and continued during the treatment period. If no classification to prior and/ or concomitant can be done, the medication will be considered as both prior and concomitant. Concomitant medications will be listed.

SARS-CoV2 test results and antibodies will be listed.

10. EFFICACY ANALYSES

Not applicable. See Section 14.

10.1 Handling of Dropouts or Missing Data

10.1.1 Missing Safety Data

When tabulating AE data, partial dates will be imputed as follows.

- If the day of the month is missing, the onset day will be set to the first day of the month unless it is the same month and year as study treatment. In this case, to conservatively report the event as treatment-emergent, the onset date will be assumed to be the first date of treatment.

- If the onset day and month are both missing, the day and month will be assumed to be January 1, unless the event occurred in the same year as the study treatment. In this case, the event onset will be coded to the first date of treatment in order to conservatively report the event as treatment-emergent. A missing onset date will be coded as the first day of treatment.
- Listings will present all data as reported (i.e., without imputations).

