**Table 1: Schedule of Assessments**

	Screening Period		Treatment Period			Follow-Up
	Screening	Run-In	Baseline	Study Visit	End of Treatment/ Early Termination 	End of Study
Study Day	-30 to -15	-14 to -1	1 ±2	7 ±2	14 ±2	28±3
Study Week	-4 to -2	-2 to -1		1	2	4
Visit Location	Clinic	Phone option	Clinic	At home option	At home option	Clinic
Events						
Informed consent form signed	X					
Review inclusion/exclusion criteria & medical history	X		X			
Demographics	X					
Physical examination 	X		X			X
Randomization			X			
Height and weight 	X		X			X
Concomitant medications	X	X	X	X	X	X
Adverse event monitoring	X	X	X	X	X	X
HIV and hepatitis tests	X					
Pregnancy test (urine)	X		X			X
Drugs of abuse screening 	X		X			X
Vital signs 	X		X	X	X	X
12-lead ECG	X		X			X
Hematology	X		X		X	X
Total serum chemistry 	X		X		X	X
LFTs only				X		
Urinalysis	X		X		X	X
COVID-19 testing 	X		X		X	X
E2, SHBG, LH, FSH 	X 		X	X	X	X
Endometrial biopsy 						X
Transvaginal ultrasound 		X				X
Mammogram 		X				

	Screening Period		Treatment Period			Follow-Up	
	Screening	Run-In	Baseline	Study Visit	End of Treatment/ Early Termination 	End of Study	
Study Day	-30 to -15	-14 to -1	1 ±2	7 ±2	14 ±2	28±3	42±3
Study Week	-4 to -2	-2 to -1		1	2	4	6
Visit Location	Clinic	Phone option	Clinic	At home option	At home option	Clinic	At home option
Events							
Pap smear and HPV testing 	X						
Plasma PK collection 				X		X	
Dispensing of medication			X				
Drug accountability and compliance check				X	X	X	
Dosing of medication in clinic 			X			X	
Recording of VMS frequency/severity in daily HF eDiary 							→
Recording of body temperature in daily eDiary 							→
HFRDIS			X		X	X	
ISI			X			X	

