13. SAFETY ANALYSES

All safety analyses will be based on the safety population defined as all randomized subjects who took at least one dose of study drug, will be descriptive only, and will be presented by treatment group. No inferential testing will be performed. Missing safety data will not be imputed.

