13.2 Adverse Events

All AE summaries will be restricted to treatment-emergent AEs (TEAEs), which are defined as those AEs that occurred after dosing and those existing AEs that worsened after start of dosing. If it cannot be determined whether the AE is treatment-emergent due to a partial onset date, then it will be counted as such. Verbatim terms in the eSource forms will be mapped to preferred terms and system organ classes using the Medical Dictionary for Regulatory Activities (MedDRA) (version 23.0).

Each AE summary will be displayed by treatment group. Summaries that are displayed by system organ class and preferred terms will be ordered by descending subject count in the total column by system organ class and preferred term. Summaries of the following types will be presented:

- Overall summary of TEAEs.
- Subject incidence of TEAEs and total number of unique TEAEs by MedDRA system organ class and preferred term.
- Subject incidence of TEAEs of special interest and total number of unique TEAEs by MedDRA system organ class and preferred term.
- Subject incidence of treatment-related TEAEs and total number of unique TEAEs by MedDRA system organ class and preferred term.
- Subject incidence of serious TEAEs and total number of unique serious TEAEs by MedDRA system organ class and preferred term.

- Subject incidence of TEAEs leading to study discontinuation and total number of unique TEAEs leading to study discontinuation by MedDRA system organ class and preferred term.

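### The rule for incomplete AE dates in SAP 10.1.1 ignores the AE end date, so an event known to have ended before dosing can be tabulated as treatment-emergent

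*SAP*

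**What the plan says.** SAP 10.1.1 (Missing Safety Data) applies when AE data are tabulated. It has three routes to a first-dose onset:

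- **Day missing.** By default "the onset day will be set to the first day of the month unless it is the same month and year as study treatment". If the month and year do match, "In this case, to conservatively report the event as treatment-emergent, the onset date will be assumed to be the first date of treatment".
- **Day and month missing.** The default is 1 January of the recorded year. If the year is that of study treatment, "the event onset will be coded to the first date of treatment in order to conservatively report the event as treatment-emergent".
- **Whole date missing.** "A missing onset date will be coded as the first day of treatment".

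The section adds that listings show dates as reported, without imputation.

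SAP 13.2 restricts every AE summary to TEAEs, defined as "those AEs that occurred after dosing and those existing AEs that worsened after start of dosing". For incomplete dates it says: "If it cannot be determined whether the AE is treatment-emergent due to a partial onset date, then it will be counted as such".

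The introduction to SAP Section 13 says: "Missing safety data will not be imputed". The protocol synopsis, under Missing data, has the milder form: no imputation of missing safety endpoints unless specified otherwise.

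Protocol Table 1 marks "Adverse event monitoring" at Screening (Day -30 to -15) and Run-in (Day -14 to -1), as well as at the later visits.

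**The concern.** AE recording starts up to 30 days before the first dose, so the database can hold events that began and ended before any study drug was taken. For such an event with an incomplete onset date, the end date alone can settle that it is not treatment-emergent. The 10.1.1 rule never consults it. Followed as written, the rule produces a derived onset later than the recorded end and puts the event in the TEAE tables.

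An event that ended before dosing neither occurred after dosing nor could have worsened after it, so the result conflicts with the 13.2 definition. The SAP does not say which section prevails, and two programmers could classify the same event differently.

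The TEAE tables matter more than usual here. The study was stopped early for safety reasons (SAP 13.1 and 14). Neither efficacy nor PK data will be tabulated (SAP 12 and 14), so the AE tables are among the main remaining outputs, and SAP 14 describes the number of randomized subjects as limited. An affected event would also appear in the listing as ended before first dose and in the table as emergent, although SAP Section 6 calls for consistency between tables and listings.

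**Working it through.** The plan states no figure on this point, so there is none to reproduce. The check applies the rule literally.

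**Step 1. Worked dates.** The dates are assumed for illustration. First dose is 20JAN2021.

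| Recorded onset | Recorded end | Onset under 10.1.1 | Treatment-emergent? | Onset after end? |
|---|---|---|---|---|
| JAN2021, day missing | 10JAN2021 | 20JAN2021 | Yes | Yes, by 20 − 10 = 10 days |
| 2021, day and month missing | 10JAN2021 | 20JAN2021 | Yes | Yes, by 10 days |
| Fully missing | 10JAN2021 | 20JAN2021 | Yes | Yes, by 10 days |
| DEC2020, day missing | 10JAN2021 | 01DEC2020 | No | No |
| FEB2021, day missing | 20FEB2021 | 01FEB2021 or 20JAN2021 | Yes either way | No |

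The first three rows show the error. The fourth shows that the rule does use the recorded month, since a December event stays pre-treatment. The fifth has two answers because 10.1.1 does not say whether study treatment means the first dose or the whole dosing period. Under the period reading the onset is moved to a month in which the event is known not to have started, but the event is post-dose on either reading and its TEAE status does not change.

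**Step 2. How often the rule misclassifies an event that qualifies.** These inputs are assumptions, not taken from the documents:

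- first-dose dates are every day from 01SEP2020 to 11FEB2021, which is 164 dates;
- true onset is each of Day -30 to -1;
- AE duration L is 1, 3 or 7 days;
- only events that ended before first dose are kept;
- study treatment is read as the month or year of first dose.

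Events enumerated = 164 × (31 − L), which gives 4,920, 4,592 and 3,936. Share misclassified = events given a first-dose onset ÷ events enumerated.

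| What is missing | L = 1 | L = 3 | L = 7 |
|---|---|---|---|
| Day | 2,320/4,920 = 47.2% | 2,010/4,592 = 43.8% | 1,462/3,936 = 37.1% |
| Day and month | 4,455/4,920 = 90.5% | 4,130/4,592 = 89.9% | 3,492/3,936 = 88.7% |
| Whole date | 100% | 100% | 100% |

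With a check that blocks first-dose imputation when the recorded end precedes first dose, the count is 0 in all nine cells.

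Every share is conditional on three things: the onset date is incomplete, the end date is known, and the event ended before first dose. The documents give no rate for any of these, so the shares cannot be turned into a number of events.

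**Step 3. Weight of one event.** About 33 subjects per arm were planned (SAP Section 5), and the study stopped early. One subject wrongly added to an incidence row moves that arm's percentage by 1/33 = 3.0 points at the planned size, and by more in a smaller arm. If the subject already counts in that row, only the event count changes.

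**The case against.** The best defence is that 13.2, the section that defines TEAEs, already gives the right answer. Its default covers only events whose status cannot be determined, and a pre-dose end date determines it. A programmer working from 13.2 would have grounds to exclude the event. That is fair, and it is why the error is tied to 10.1.1 as written. But 10.1.1 is unconditional, no order of precedence is given, and the QC list in SAP Appendix B asks whether SAP derivation rules were followed, so a literal implementation would satisfy that item.

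The rule is also openly conservative, and over-inclusion may be what one wants in a study stopped for safety. That holds for events of unknown timing. It does not justify including an event whose recorded end date shows it was over before dosing.

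The consequences are limited, and these points stand. The rule is identical in both arms. Section 13 plans descriptive summaries with no inferential testing. Reported dates stay visible in the listings, and the output review in Appendix B looks for invalid values. Similar pre-dose events added to both arms would pull a ratio towards one but would not systematically shift a difference in event counts.

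Four stronger readings are tempting, and the documents do not support them:

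- *The rule ignores the recorded onset month.* It does not. The first-dose assignment applies only after month and year have been compared with study treatment.
- *The vague term study treatment also corrupts the TEAE tables.* It does not. A later month of the dosing period is after first dose on either reading, and Appendix C lists no time-to-onset or by-period AE table.
- *Section 13 forbids what 10.1.1 does.* The general sentence is reasonably read as qualified by the specific rule for AE dates, in line with the protocol's allowance for exceptions.
- *Close to half of all screening AEs would be misclassified.* The 37% to 47% applies only to events that meet all the conditions in Step 2.

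**Conclusion.** The concern holds in a narrow form. SAP 10.1.1 assigns a first-dose onset in three situations without looking at the end date. As written, it can turn an event known to have resolved before dosing into a TEAE with an onset after its end, in conflict with 13.2.

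The size is minor and cannot be fixed in absolute terms. Among events that qualify, the literal rule misclassifies 37% to 47% when the day is missing, about 89% to 91% when day and month are missing, and all of them when the whole onset date is missing, under the assumed dose dates and durations. The number of qualifying events is not in the documents and may be zero. The conclusion assumes that AE end dates are recorded and that 10.1.1 is programmed literally. It does not imply a biased comparison between arms or a fault in how events of truly unknown timing are treated.

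**What to change.** 1. Add one sentence to SAP 10.1.1, for example: *If the recorded end date, complete or partial, shows that the AE ended before the first dose, the AE is not treatment-emergent and its onset is not imputed to the first dose date.* This also settles the conflict with 13.2.
2. In the month and year comparisons of 10.1.1, replace study treatment with first dose of study treatment. This removes the two possible onsets in the FEB2021 row and leaves TEAE status unchanged.
3. Optional tidying: in the no-imputation sentence of Section 13, refer to the AE date rule in 10.1.1 as the exception.

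The cost is one new sentence, one wording change and a few lines of code in the AE derivation. Events whose timing is truly unknown remain treatment-emergent, so the conservative intent is kept. The change is best made before the blind is broken, since SAP Section 6 treats later analyses as post hoc. If that point has passed, the handling can be recorded in the clinical study report as a deviation from the plan, as SAP Section 1 provides.

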10.2 Interim Analysis and Data Monitoring

An independent Data Monitoring Committee (DMC) will be established for this study. Members of the DMC will be independent of the study Investigators and the sponsor. The DMC will comprise of relevant medical experts in the following disciplines: women's health specialist with experience in management of and clinical research in vasomotor symptoms, clinical drug development in women's health, hepatology. The DMC will also include an independent statistician who will have access to the clinical database and the randomization code. The DMC will review safety data at regular intervals according to the DMC Charter. The DMC Charter will establish meeting frequency, scope and method of data review, maintenance of blind, and the decision-making process, prior to the start of the study. In the event that potential safety issues are identified, the DMC may recommend modification of the study design or study termination, which will be communicated to the Investigators, Institutional Review Boards/Independent Ethics Committees (IRBs/IECs), and regulatory agencies by the Sponsor, in accordance with legal and regulatory requirements. The DMC Charter is finalized in synSOJd_DMC Charter_V2_16JUL2020_Final.doc.pdf.

There are no planned interim efficacy analyses for this study.

10.3 Multicenter Studies

This is multicenter study, with approximately 20 centers participating in the study. Approximately 66 subjects will be randomized, leading to approximately 3 subjects per center.

This expected low number of subjects at some centers does not allow center to be included as a covariate in the statistical model.

11. METHODS OF EFFICACY ANALYSIS

Not applicable. See Section 14.

12. PHARMACOKINETIC ANALYSES

PK sampling will occur prior to dosing on Day 28 (EOT), and on Day 7, also prior to dosing if possible. Trough plasma concentrations of SJX-653 and its 2 metabolites M2 and M3 in steady state will be reported by the PK laboratory. PK data will not be summarized or tabulated.

13. SAFETY ANALYSES

All safety analyses will be based on the safety population defined as all randomized subjects who took at least one dose of study drug, will be descriptive only, and will be presented by treatment group. No inferential testing will be performed. Missing safety data will not be imputed.

13.1 Extent of Exposure

Study drug exposure based on expected exposure will be summarized by treatment group. Expected exposure will be derived as follows:

- Subjects who complete the Day 28/EOT visit: $(64 \text{ tablets dispensed} - \text{number tablets returned} - \text{number tablets lost}) / (2*28)$
- Subjects who prematurely discontinue prior to Day 28/EOT: $(64 \text{ tablets dispensed} - \text{number tablets returned} - \text{number tablets lost}) / 2*(12FEB2021 - \text{date of first dose} + 1)$

Note: 12FEB2021 is the date of sponsor notification of sites of study termination for safety reasons.

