14. CHANGES TO PROTOCOL-SPECIFIED ANALYSES

Based on the DMC meeting on Thursday Feb 11th and a subsequent internal company meeting, Sojournix terminated the SJX-653-006 study early. At the time of termination, sites were

informed to stop screening and withdraw all subjects from the study. Subjects on treatment were notified to stop dosing immediately.

Due to limited number of randomized subjects, select safety data will be summarized as outlined in Section 13. Efficacy data will not be summarized or tabulated.

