16. APPENDICES

APPENDIX A: PRESENTATION OF DATA AND PROGRAMMING SPECIFICATIONS

General

- Specialized text styles, such as bold, italics, borders, shading, superscripted and subscripted text will not be used in tables, figures, and data listings unless they add significant value to the table, figure, or data listing.
- Only standard keyboard characters are to be used in tables and data listings.
- Special characters, such as non-printable control characters, printer-specific, or font-specific characters, will not be used on a table, figure, or data listing.
- Hexadecimal character representations are allowed (e.g., μ , a, β).
- All footnotes will be left justified and at the bottom of a page. Footnotes should be used sparingly and must add value to the table, figure, or data listing.

Tables

- Means and medians will be presented to one more decimal place than the raw data. Standard deviations will be presented to two more decimal places than the raw data. Minimums and maximums will be reported with the same number of decimal places as the raw data.
- Percentages will be presented with two decimal places.
- For frequency counts of categorical variables, categories whose counts are zero will be displayed for the sake of completeness. For example, if none of the subjects discontinue due to “lost to follow-up,” this reason will be included in the table with a count of 0. Categories with zero counts will not have zero percentages displayed.
- Percentiles (e.g., 25%, 75%) should be presented to one decimal place more than the raw/derived data.
- The first footnote will be “Source: xxx”, where xxx indicates the source listing number(s) and/or source dataset(s) (e.g., ADaM).

Listings

- If not otherwise specified, all data listings will be sorted by treatment, center, subject number, visit, and date/time as appropriate.
- All date values will be presented in a SAS date (e.g., 29AUG2001) format.
- All observed time values will be presented using a 24-hour clock HH:MM:SS format (e.g., 01:35:45 or 11:26). Seconds will only be reported if they were measured as part of the study.

Standard Calculations

Variables requiring calculation will be derived using the following formulas:

- **Days** – A duration expressed in days between one date (*date1*) and another later date (*date2*) is calculated using the formulas noted below:
duration in days = $date2 - date1 + 1$

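### SAP 13.1: the exposure formula for early discontinuers lacks its outer bracket, and its fixed end date of 12FEB2021 suits only subjects still on treatment when sites were notified

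*SAP*

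**What the plan says.** SAP Section 13.1 opens with: "Study drug exposure based on expected exposure will be summarized by treatment group". It then gives two derivations with the same numerator: 64 tablets dispensed, less those returned and those lost.

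- Subjects who complete the Day 28/EOT visit: the numerator is divided by (2×28), with the product in brackets.
- "Subjects who prematurely discontinue prior to Day 28/EOT": the numerator is followed by a slash, then "2*(12FEB2021 - \text{date of first dose} + 1" and a single closing bracket. That bracket closes the date difference. No bracket encloses the product of 2 and the number of days.

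A note explains the fixed date: "12FEB2021 is the date of sponsor notification of sites of study termination for safety reasons". SAP Section 14 adds what happened at termination: "Subjects on treatment were notified to stop dosing immediately".

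Section 13.1 gives no other end date, no cap at the 28-day plan, and no restriction of the second formula to subjects withdrawn at termination. The result feeds Table 14.3.5, the only exposure summary in the Appendix C index.

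**The concern.** There are two separate problems.

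First, the early-discontinuer formula as printed is not a ratio of used to expected tablets. Its values are not on the completers' scale, so the two groups could not share one summary.

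Second, with the bracket restored, the calendar date on which sites were notified stands in for each subject's end of dosing. That is right for a subject dosing up to that day. For anyone who stopped earlier for her own reasons, the divisor counts days when she was no longer taking drug. Her value then depends on when she happened to start as well as on what she took. Section 13.1 also does not say whether the ratio means compliance while on drug or the fraction of the planned course taken.

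The trial was stopped for safety reasons, and SAP Section 12 says the PK data will not be tabulated. Table 14.3.5 is therefore the reader's only summary of how much drug each arm received.

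**Working it through.** **Inputs.** The protocol synopsis gives 20 mg once daily for 4 weeks and a 10 mg tablet, so 20/10 = 2 tablets a day. The planned course is 2 × 28 = 56 tablets. SAP 13.1 gives 64 tablets dispensed and the date 12FEB2021. First-dose and stopping dates below are illustrative, because the documents give none, and full adherence while dosing is assumed.

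**Notation.** T = tablets used. D = 12FEB2021 − date of first dose + 1. s = days actually dosed, so T = 2s.

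**Intended scale.** The SAP gives no worked value to reproduce. The completer line fixes the scale: full adherence gives 56/(2 × 28) = 1.00.

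**Part 1, the bracket.** With division and multiplication of equal precedence, taken left to right, the printed form is (T/2) × D. The bracketed form is T/(2 × D). For a subject dosed through 12FEB2021, T = 2D:

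| D (days) | T | Printed: (T/2) × D | Bracketed: T/(2 × D) |
|---|---|---|---|
| 7 | 14 | 49 | 1.00 |
| 14 (first dose 30JAN2021) | 28 | 196 | 1.00 |
| 21 | 42 | 441 | 1.00 |
| 27 | 54 | 729 | 1.00 |

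The printed form inflates the value by D².

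**Part 2, the end date.** Bracketed, a subject who stopped after s days scores 2s/(2D) = s/D. For s = 7 (14 tablets):

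| First dose | D | Expected tablets (2D) | Ratio |
|---|---|---|---|
| 04JAN2021 | 40 | 80 | 14/80 = 0.175 |
| 16JAN2021 | 28 | 56 | 14/56 = 0.25 |
| 30JAN2021 | 14 | 28 | 14/28 = 0.50 |

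The same seven days are 14/14 = 1.00 as on-treatment compliance and 14/56 = 0.25 as a fraction of the 28-day plan.

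**The missing cap.**

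- First dose 15JAN2021: D = 29, so 58 tablets expected against 56 planned.
- First dose 12JAN2021: D = 32, so 64 expected, equal to the 64 dispensed.
- First dose 11JAN2021: D = 33, so 66 expected against 64 dispensed.

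For an early stopper first dosed on or before 15JAN2021 the ratio is neither compliance nor fraction of plan. On or before 11JAN2021 it could not reach 1.00 even if every dispensed tablet were taken.

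**The case against.** **The bracket is a slip that QC would catch.** The completer line directly above shows the intent. A value of 196 beside values near 1 should not survive the senior statistical review in SAP Section 6 or the range check in Appendix B. Appendix B also checks that percentages stay within 100%, which would help if the ratio is shown as a percentage. Detection is indeed likely. But Appendix B checks programs and datasets against the SAP, so the wrong formula is part of the reference standard. The two-subject manual calculation sits under Listings, and Appendix C has no exposure listing. A bracket lost in text extraction cannot be fully excluded, although the printed brackets balance and the adjacent line kept its own.

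**The end-date problem may affect nobody.** The SAP is dated 02APR2021, after termination, and its authors may have known that every early discontinuer was on treatment at notification. Section 9.1 does plan to report "the number of subjects discontinuing the study, and the primary reason for discontinuation", and Section 13.2 plans "Subject incidence of TEAEs leading to study discontinuation". Neither shows that an earlier stop occurred, since under Appendix A "categories whose counts are zero will be displayed for the sake of completeness". The 12% drop-out rate is a planning assumption and says nothing about this cohort. This objection stands, and is why the second part is conditional.

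**Counting expected tablets to study stop could be deliberate.** It shows an early stopper as having received less drug than expected, whereas her own end date gives her 1.00 and hides the short course. The second half of this is fair, and it calls for reporting duration alongside the ratio. The first half does not rescue the rule: 13.1 states no such convention, and without a cap the divisor can exceed both the planned course and the tablets dispensed.

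**Conclusion.** The concern holds and is minor.

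The bracket error needs no assumption about the data: the rule as printed is wrong, by a factor of D² (196 for 1.00 at 14 days).

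The end-date point holds as a property of the rule, which covers all early discontinuers without restriction or cap. Whether it changes any reported value depends on whether anyone stopped before 12FEB2021. That number is not given and may be zero. If it is not zero, an adherent early stopper's ratio becomes s/D instead of 1.00, for example 0.175 to 0.50 for seven days' dosing on the dates shown.

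The consequence stays within one descriptive table. SAP Section 13 plans no inferential testing, efficacy is not analysed, and no adverse event or liver output uses exposure as a denominator.

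**What to change.** 1. Write the divisor as (2 × (end date − date of first dose + 1)), with the outer bracket.
2. Establish whether every early discontinuer was on treatment at notification. If so, say so in Section 13.1; the divisor then needs only the bracket.
3. If not, keep 12FEB2021 for subjects on treatment at notification. For the others use the subject's own last dose date, no later than 12FEB2021. If that date is not recorded, use the date she discontinued treatment, not the date she left the study; footnote 1 to the protocol's Table 1 treats the two as distinct.
4. State that the corrected ratio measures compliance, and add days on treatment by arm using the Days formula in SAP Appendix A, so that short exposure remains visible.

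The cost is one line and one sentence in Section 13.1, one derivation and one summary row. The available documents do not confirm that a last dose date is captured, which is why a fallback is given.
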